### 12.3. Figures

Figure Number	Title
1	Mean (+/- SD) Concentrations of WBC Cystine (nmol half Cystine/mg protein) versus Time (Collected Visit) PK/PD Population

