#### For subjects who completed Study RP103-03:

- Screening Visit: The RP103-04 Screening visit occurred simultaneously with the RP103-03 Period 2 Day 7 End of Study (EOS) visit. These subjects continued RP103 Q12H treatment at the last dose level prescribed during their participation in Study RP103-03.
- Monthly Study Visits are only for subjects who completed Study RP103-03 and began within 1 month ( $\pm$  7 days) after study entry. Each subject completes a minimum of six (6) consecutive monthly visits.
- Quarterly Study Visits commence for each subject  $\geq$  1 month and  $<$  4 months after the subject has completed at least six (6) consecutive Monthly visits. Each Quarterly visit takes place by the middle of the first month ( $\pm$  7 days) of each calendar quarter (i.e. January 15, April 15, July 15 and October 15).
- End of Study (EOS) Visit is conducted within 7 ( $\pm$  2) days from the last completed study visit or from the date of decision to terminate.

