#### For subjects who did not complete Study RP103-03:

- Screening Visit which may occur up to 28 days prior to Day 1.

- Dose Confirmation Period (Days 1-5) which includes three (3) study visits over five (5) days.
  - Day 1 includes a morning study visit while the subject is fasted, with pre-dose blood samples collected for trough cysteamine and peak white blood cell (WBC) cystine determination while the subject is still taking Cystagon®. RP103 treatment regimen begins at the clinic on the morning of Day 1, administered Q12H at a starting total daily RP103 dose equal to 70% of the Screening total daily Cystagon® dose. Subjects leave the clinic for Days 2-3 and take RP103 as instructed.
  - Days 4 and 5 each include a morning study visit; RP103 Q12H treatment regimen continues.
- Quarterly Study Visits commence for each subject  $\geq$  1 month and  $<$  4 months after enrollment in the study. Each quarterly visit takes place by the middle of the first month ( $\pm$  7 days) of each calendar quarter (i.e., January 15, April 15, July 15 and October 15).
- End of Study (EOS) Visit will be conducted within 7 ( $\pm$  2 days) from the last completed study visit or from the date of decision to terminate.

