- d. A minimum of 6 consecutive Monthly ( $\pm$  1 week) Visits will be conducted for all subjects who completed Study RP103-03 prior to enrolling in study RP103-04. Subjects who did not complete Study RP103-03 will not attend Monthly visits.
- e. Quarterly visits will take place by the middle of the first month ( $\pm$  7 days) of each calendar quarter (i.e., January 15, April 15, July 15 and October 15) so that samples can be analyzed on the bioanalytical lab's quarterly analysis schedule.
- f. The End of Study visit will be conducted within 7 ( $\pm$  2 days) from the last completed study visit or from the date of decision to terminate.
- g. For subjects that completed the RP103-03 Study, data can be obtained from the RP103-03 Screening visit.
- h. For subjects that completed the RP103-03 Study, data can be obtained from the RP103-03 End of Study Visit.
- i. Physical examinations are to include standard physical assessments together with a neurological and skin examination.
- j. Clinical laboratory (chemistry and hematology) and urinalysis samples will be collected at Screening (if required) and at Monthly and Quarterly visits, thereafter and at the End of Study (EOS) visit.
- k. 12-lead ECG will be collected within 30 minutes prior to Study drug administration at Screening (if required) and at Monthly and Quarterly visits, thereafter and at the End of Study (EOS) visit. For subjects that did not complete Study RP103-03, the 12-lead ECG will also be conducted at approximately 3 hours ( $\pm$  15 minutes) post RP103 dose on Day 1.
- l. Vital signs will be measured within 30 minutes prior to Study drug administration at Screening (if required) and at Monthly and Quarterly visits, thereafter and at the End of Study (EOS) visit. For subjects that did not complete Study RP103-03, vital signs will also be repeated 30 minutes prior to Study drug administration on Day 1.

- o. RP103 will be administered Q12H daily. Subjects that completed Study RP103-03 will continue to receive their Q12H RP103 dose determined during that Study. For subjects that did not complete Study RP103-03, the first dose of RP103 will be given on Day 1, with a starting Q12H RP103 dose at a total daily dose which is 70% of their total daily dose Cystagon® dose.

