#### 4.2.9. Visit Windows

The visit schedule in Study RP103-04 differed according to whether a subject entered the study after completing Study RP103-03 or entered the study without having previously participated in Study RP103-03 (i.e., Subjects  $\leq$  6years of age and kidney transplant recipients). This difference in visit schedule resulted in each Quarterly visit for subjects from Study RP103-03 occurring, on average, approximately 6 months later in the study than the corresponding Quarterly visit for subjects who did not previously participate in Study RP103-03. For example, the Quarterly 1 visit of a subject from Study RP103-03 generally occurred at approximately 0.75 years in the study, while the Quarterly 1 visit for a subject not previously participating in Study RP103-03 generally occurred at approximately 0.25 years in the study. Two approaches were taken in the analysis to aligning visits for summarization over time:

1. **Collected Visits:** Scheduled Visits (i.e., the visit as recorded on the case report form) were assigned to what is referred to as “Collected Visits” (see
2. Table 2). Summarization using Collected Visits will help to address the approximate 6-month difference between the Quarterly visits for subjects from Study RP103-03 compared to subjects who had not participated in Study RP103-03.

**Table 2: Definition of “Collected Visits” for Subjects Not Previously Participating in Study RP103-03 (Subjects  $\leq$  6 Years of Age and Kidney Transplant Recipients)**

Scheduled Visit		Assigned “Collected Visit” (Label)
Scheduled Visit Number	Scheduled Visit Name	
14	Quarterly 1	Monthly 3
15	Quarterly 2	Monthly 6
16	Quarterly 3	Quarterly 1
17	Quarterly 4	Quarterly 2
18	Quarterly 5	Quarterly 3
19	Quarterly 6	Quarterly 4
20	Quarterly 7	Quarterly 5
21	Quarterly 8	Quarterly 6
22	Quarterly 9	Quarterly 7
23	Quarterly 10	Quarterly 8
24	Quarterly 11	Quarterly 9

Scheduled Visit		Assigned “Collected Visit” (Label)
Scheduled Visit Number	Scheduled Visit Name	
25	Quarterly 12	Quarterly 10
26	Quarterly 13	Quarterly 11
27	Quarterly 14	Quarterly 12
Continues in this pattern for however many Quarterly visits occur		

The table only displays Collected Visits for which the name/label differs from that of the Scheduled Visit.

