### 9.1. Study Drug Exposure

Duration of study drug exposure will be calculated as the duration from the date of first dose of RP103 in Study RP103-04 to the date of last dose as:

Exposure (days) = (Last Dose Date – First Dose Date + 1) – number of days dosed with Cystagon

Duration of exposure will be summarized for each subpopulation and overall using descriptive statistics. The number and percentage of subjects with duration of exposure in each category ( $\leq$  12 months,  $>$  12 months and  $\leq$  24 months,  $>$  24 months and  $\leq$  36 months,  $>$  36 months and  $\leq$  48 months,  $>$  48 months and  $\leq$  60 months, and  $>$  60 months) will also be summarized.

The mean RP103 dose (mg/m^2/day) will be summarized over time using collected visits.

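### In the 'overall' Collected Visit level summaries, and in Figure 1 if it is pooled, the cohort mix alternates from label to label over roughly the first nine months, so the mean combines change over time with change in who is measured

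*SAP*

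**What the plan says.** SAP 4.2.9 sets up Collected Visits because the two entry routes have different schedules: "Summarization using Collected Visits will help to address the approximate 6-month difference between the Quarterly visits". SAP Table 2 relabels new entrants' Quarterly 1 as Monthly 3 and Quarterly 2 as Monthly 6, and moves each later Quarterly visit back by two. Visits missing from that table keep their names: "The table only displays Collected Visits for which the name/label differs from that of the Scheduled Visit".

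The schedules differ as follows.

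- **RP103-03 completers** (SAP 2.1): "Each subject completes a minimum of six (6) consecutive monthly visits". SAP Table 1.1 allows 6 to 9.
- **New entrants** (SAP Table 1.1, footnote d): "Subjects who did not complete Study RP103-03 will not attend Monthly visits". They have instead, under SAP 2.1, a "Dose Confirmation Period (Days 1-5) which includes three (3) study visits over five (5) days".

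WBC cystine and plasma cysteamine are summarized for each subpopulation and overall, on both Collected and Analysis Visits (SAP 8.1, 8.2). Safety data are also summarized by subpopulation and overall (SAP 9). Mean RP103 dose "will be summarized over time using collected visits" (SAP 9.1). Laboratory, vital sign and ECG values are shown by collected visit, as levels and as change from baseline (SAP 9.3-9.5). SAP 4.2.4 plans no covariate adjustment. The only figure listed in SAP 12.3 is "Mean (+/- SD) Concentrations of WBC Cystine (nmol half Cystine/mg protein) versus Time (Collected Visit) PK/PD Population", and its title names no split by subpopulation.

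**The concern.** The relabelling lines up the two cohorts in time, but it places new entrants at only two of the Monthly labels. An unadjusted overall mean read from left to right then compares different groups of people at neighbouring labels. If the cohorts differ in level, the overall line moves at Monthly 3, returns at Monthly 4, moves again at Monthly 6, and so on, with every patient stable.

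The documents give reasons to expect level differences. Subpopulation B is aged 6 or under (SAP 3.1), while the RP103-03 ITT patients averaged 11.7 years, 36.0 kg and 1.17 m² (Protocol 4.2.2, Table 2). Subpopulation C is renal transplant recipients, while RP103-03 took patients with native kidney function. RP103-03 enrolled patients with WBC cystine below 2, while the current RP103-04 criteria for new entrants contain no cystine limit.

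At stake is how the early part of the long-term displays is read: a change in composition could be taken for a change on drug. SAP 4.2.9 warns of fluctuating sample sizes for Analysis Visits and implies that Collected Visits are steadier. It does not mention this alternation.

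**Working it through.** **1. The plan's own figure.** SAP 4.2.9 gives an offset of about 6 months: "Quarterly 1 visit of a subject from Study RP103-03 generally occurred at approximately 0.75 years in the study", against about 0.25 years for a new entrant.

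- Completers: six Monthly visits plus 1 to 4 months = 7 to 10 months, midpoint 8.5 months (0.71 years).
- New entrants: 1 to 4 months after enrolment, midpoint 2.5 months (0.21 years).
- Difference: 8.5 − 2.5 = 6.0 months.

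This agrees with the SAP and with the two-visit shift in Table 2. The alignment in time is sound.

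**2. Who is scheduled at each label.**

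| Collected Visit | Completers | New entrants |
|---|---|---|
| Screening | yes | yes |
| Day 1, 4, 5 | no | yes |
| Monthly 1, 2 | yes | no |
| Monthly 3 | yes | yes |
| Monthly 4, 5 | yes | no |
| Monthly 6 | yes | yes |
| Monthly 7-9 | yes (those who have them) | no |
| Quarterly 1 onward | yes | yes |
| EOS | yes | yes |

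The Day 1 PK/PD sample precedes the first RP103 dose, so under SAP 4.2.1 it may appear as Baseline. Days 4 and 5 remain new-entrant-only labels.

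**3. Size of the step.** Let w be the share of new entrants at a mixed label and d the new-entrant mean minus the completer mean. Then

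overall mean = (1 − w) × completer mean + w × new-entrant mean,

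and the step when new entrants join or leave is w × d.

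The documents do not give the RP103-04 split. As an assumption, take 41 completers (43 randomized in RP103-03 less 2 withdrawn) and 60 − 41 = 19 new entrants, using the enrolment ceiling of 60. Then w = 19/60 = 0.317. The documents give no WBC cystine values for new entrants, so d is shown as a range (nmol half-cystine/mg protein):

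| d | Step, w = 0.30 | Step, w = 0.317 | Step, w = 0.50 |
|---|---|---|---|
| 0 | 0 | 0 | 0 |
| 0.2 | 0.06 | 0.063 | 0.10 |
| 0.5 | 0.15 | 0.158 | 0.25 |
| 1.0 | 0.30 | 0.317 | 0.50 |

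**4. What the pooled line would look like.** Hold both cohorts flat, with completers at 0.63 (SD 0.31), the RP103-03 per-protocol baseline, and d = 0.5:

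| M1 | M2 | M3 | M4 | M5 | M6 | M7 | Q1 | Q2 |
|---|---|---|---|---|---|---|---|---|
| 0.63 | 0.63 | 0.788 | 0.63 | 0.63 | 0.788 | 0.63 | 0.788 | 0.788 |

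If the within-cohort SD is 0.31 in both, the SD bars at mixed labels also widen, to √(0.31² + 0.317 × 0.683 × 0.5²) = 0.39. Nobody has changed. With d = 0 the line is flat.

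**5. Weight and BSA.** The same formula applies. Children aged 6 or under should pull the overall mean below a completer mean near 36 kg and 1.17 m², so a step is expected. Its net size depends on the numbers in subpopulations B and C and on the transplant recipients' body size, none of which is given.

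**The case against.** Much of the remedy is already planned. New entrants are the children aged 6 or under and the transplant recipients (SAP 4.2.9), so the A, B and C columns separate them from completers. The number of subjects is a specified statistic for PD, PK, laboratory, vital sign and ECG tables, so an attentive reader would see it change. Change-from-baseline columns cancel any constant difference in level. All of this stands, and it confines the point to overall level values.

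Several stronger readings are tempting, and the documents do not support them.

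- A reader might infer that new entrants appear only at Monthly 3, Monthly 6 and Quarterly visits. They also have Screening, Day 1, Day 4, Day 5 and EOS visits.
- A reader might infer that the overall curve follows cohort mix and not time on RP103. It combines the two, and how much is artefact depends on d.
- A reader might take it as settled that Figure 1 is one pooled line. Its title is silent and the table list in SAP 12 is blacked out.
- A reader might extend the problem to the whole long-term trend. From Quarterly 1 both cohorts are scheduled at every label, at matched times. Later drift in the mix would come from dropout or differing follow-up, as in any pooled display.
- A reader might set the step against the 0.3 non-inferiority margin of RP103-03. That margin governed a crossover treatment contrast. This single-arm study makes no such comparison, and SAP 4.2.1 treats any testing as exploratory.

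On WBC cystine, all patients share the same dose-review criterion of below 1 (Protocol 8.5), which makes a sustained difference as large as 1.0 speculative.

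The Analysis Visit tables do not answer what remains. Their mix also varies by month, and none is specified for dose, laboratory, vital sign or ECG data.

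**Conclusion.** The point holds in a limited form and is minor. The alternating mix follows directly from the SAP's own schedule and Table 2 and needs no assumption. Its effect on overall level means is w × d. A step is expected for weight and BSA. For WBC cystine it is about 0.16 under the assumed 41/19 split and an assumed difference of 0.5, and zero if the cohorts do not differ. Plasma cysteamine, mean dose and the level columns for laboratory, other vital sign and ECG values are exposed in the same way, by an amount the documents do not allow one to estimate. Figure 1 is affected only if it is drawn pooled.

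**What to change.** - **SAP 12.3:** state that Figure 1 is drawn as separate lines for subpopulations A, B and C, with n under each visit.
- **SAP 8.1, 8.2, 9.1 and 9.3-9.5:** limit overall Collected Visit summaries of level values to the labels both schedules share: Baseline, Monthly 3, Monthly 6, Quarterly n and EOS. Show Monthly 1, 2, 4, 5 and 7-9 for completers only, and Days 1, 4 and 5 for new entrants only.

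The cost is SAP wording and table and figure shells, with no new data. The downside is that there is no overall value at labels attended by one cohort. Little is lost, because an overall value there only repeats that cohort's own result. The change removes the scheduled alternation, but not later drift from dropout or differing follow-up. The n under each visit would make that visible in Figure 1.
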